## **Randomization**

After baseline assessment, patients will be randomly assigned to either a supervised strength exercise intervention or usual care with a 1:1 allocation as per a computer-generated randomization schedule, stratified by hospital site (Aarhus, Odense, Aalborg, Horsens, Hvidovre, or Melbourne).

## **Statistical interim analyses and stopping guidance**

No interim analysis or stopping guidance is planned as the interventions, supervised strength exercise, and usual care (e.g., advice to remain physically active following World Health Organization guidelines) are known to have minimal risks.

## **Timing of outcome assessments**

Outcome assessments are planned at baseline and 6 months follow-up for performance-based physical functioning tests (e.g., maximal muscle strength in the one-repetition maximum unilateral leg press, single leg jump for distance, and one leg rise test). Outcome assessments are planned at baseline, 3, 6, and 12-month follow-ups for patient-reported outcome measures and cost. See Table 1 in the study protocol.

## **STATISTICAL PRINCIPLES**

### **Confidence intervals and p-values**

Results will be expressed as between-group differences in means with 95% confidence intervals.

## **TRIAL POPULATION**

All potential participants at the hospital sites will be screened for eligibility following the inclusion and exclusion criteria.

Inclusion criteria have previously been used for diagnostic inclusion in the PhysioFIRST trial: (1) Activity- or position-related pain lasting  $\geq 3$  months; (2) Positive Flexion-Adduction-Internal Rotation (FADIR) test; (3) Cam-type FAIS; x-ray alpha angle  $> 60$  degrees or 4) Pincer-type FAIS; lateral center edge angle (LCEA)  $> 39$  degrees or cross-over sign or 5) Mixed-type FAIS; a combination of cam- and pincer-type impingement defined in inclusion criteria 3 and 4; (6) When asked, the participant states that they are

motivated to exercise twice a week for six months; (7) 18-50 years old; and (7) Body Mass Index (BMI) score < 35 (kg/m^2). Exclusion criteria were: (1) Involvement in supervised strengthening exercises targeting the hip muscles in the last 3 months before inclusion consisting of ≥ 6 supervised physiotherapy sessions; (2) Previous hip surgery or other major hip injuries in the index hip; (3) Evidence of pre-existing osteoarthritis, defined as Tönnis grade ≥ 2 or Kellgren-Lawrence ≥ 2; (4) Evidence of pre-existing osteoarthritis, defined as lateral joint space width < 3 mm; (5) Hip dysplasia, defined as a CE-angle < 25° and an acetabular index (AI) angle > 10°; (6) Comorbidities or other problems considered to prevent participation in exercise and (7) Unable to communicate in the respective languages (Danish or English) of the participating countries. Eligibility will be limited to the hip with the highest level of symptoms at baseline.

Results will be presented in a CONSORT flowchart (See Figure 1) displaying the total number of participants who were: (1) screened, (2) excluded (with reasons), (3) randomized, (4) received allocated treatment, (5) discontinued intervention (with reasons), (6) lost to follow-up (with time and reason), (7) included in ITT analysis and (8) included in the per-protocol analysis.

### **Withdrawal/follow-up**

Participants deciding to withdraw from the intervention will be asked to complete outcome assessments even though they stop attending exercise sessions or receive hip surgery.

### **Baseline participant characteristics**

The following demographic and descriptive data will be obtained at baseline and presented by randomization group: biological sex (female/male/other), gender (woman/girl/men/boy/trans/non-binary/other), age (years), height (cm), weight (kg), body mass index (kg/m^2), index hip (left/right), hip symptom duration (months), previous hip surgery (right/left/none), previous treatment due to hip symptoms (no/yes; type of treatment), bilateral symptoms (no/yes), educational level, employment status, cohabitation status, smoking status, medicine consumption (no/yes; type of medicine; frequency) and comorbidities (no/yes; diagnosis/diagnoses). Baseline participant characteristics will be presented in Table 1.

## **ANALYSIS**

### **Outcomes:**

#### **Primary outcome**

*International Hip and Outcome Tool 33 (iHOT-33).*

The primary outcome is the change in the hip-related quality of life measured using the International Hip Outcome Tool 33 (iHOT-33) (0-100, where a higher score represents a better quality of life) from baseline to 6 months. The iHOT-33 has acceptable psychometric properties and is recommended for use in active adults with hip-related pain. The iHOT-33 has a reported minimal clinically important difference of 6.1 points. The minimal important change has been reported as 8.7 and 10.0 points.

#### **Secondary outcomes**

##### *Unilateral one-repetition-maximum (1 RM) leg press*

Unilateral one-repetition-maximum (1 RM) leg press is used as a composite outcome measure for lower limb muscle strength and is measured unilaterally by a 1 RM test in a leg press resistance training machine. Results will be in kilograms.

##### *One-Leg Rise Test (OLRT)*

The OLRT is a reliable global measure of lower limb strength and endurance. The OLRT is significantly correlated with all strength measures of the hip (i.e., hip flexion, extension, abduction, adduction, internal rotation, and external rotation) in patients with FAIS. Results will be expressed as the number of repetitions, ranging from 0 to 50.

##### *Single leg-hop for distance*

The single-leg hop for distance test is a functional performance test evaluating power generation and absorption, expressed in centimeters.

##### *Adherence and exercise volume*

Adherence to the exercise sessions (i.e., session adherence reported as the number of attended sessions expressed as a % of the total number of prescribed supervised and total sessions) and exercise progression, sets, repetitions, load, rate of perceived effort (RPE), duration of the exercise session, and whether the session was conducted under supervision, will be registered by the patients as they will be instructed to keep a paper-based exercise

diary. Intensity will be reported as Rating of Perceived Effort (RPE). Volume will be expressed as the product of the total number of repetitions performed and multiplied by the external load.

#### *Patient Acceptable Symptom State (PASS)*

PASS is defined as the value beyond which patients consider themselves well, and will be assessed using a single question.

#### *Global Perceived Effect (GPE)*

GPE will be assessed for three domains; quality of life, pain, and activities of daily living on a 7-point Likert scale ranging perceived change from 'Worse, an important worsening' (worst) to 'Better, an important improvement' (best). The GPE scale asks the patient to rate how much their condition has improved or deteriorated since baseline.

#### *Dropouts:*

In instances where patients are not satisfied with how their treatment is progressing before reaching their individual goal, they will be able to have an additional consultation with their treating surgeon, where they will be treated in their best interests. There is a risk of dropout in both groups if the treatment results in insufficient improvement of symptoms. Dropout and the reason for dropout will be recorded throughout the study.

#### *Hip surgery*

The number of patients undergoing hip surgery in each intervention group will be recorded throughout the study and registered at 3, 6, and 12 months.

#### **Other outcomes**

##### *International Hip Outcome Tool 33 (iHOT-33) subscales:*

Each of iHOT-33's subscales (0-100): Symptoms and Functional Limitations, Sports and Recreational activities, Job-related concerns, and Social, Emotional, and Lifestyle concerns has been found valid in patients with hip/groin pain who were not seeking surgery and will be reported.

### *Copenhagen Hip and Groin Outcome Score (HAGOS)*

HAGOS subscales: Pain, Physical function in Sport and Recreation, and QoL (0-100, 0 equals extreme hip and groin problems and 100 equals no hip or groin problems) will be reported. HAGOS has been found valid, reliable, and responsive to assess hip and groin function in physically active adult patients.

### *The Hip Sports Activity Scale (HSAS)*

The Hip Sports Activity Scale (HSAS) is a reliable and valid tool to determine sports levels in patients suffering from FAIS. Results will be expressed from 0 (i.e., no recreational or competitive sports) to 8 (i.e., competitive sports at elite level).

### *Return to Sport (RTS) questionnaire*

Furthermore, a consensus statement on return to sport (RTS) stated that RTS should be reported in categories from no return to participation in sport through return to sport and, finally, return to performance.

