### *Tampa Scale of Kinesiophobia 17 items (TSK-17)*

The Tampa Scale of Kinesiophobia (TSK) is a valid and reliable tool to assess somatic focus and activity avoidance in patients. TSK-17 consists of 17 statements that measure pain-related fear of movement in patients with chronic musculoskeletal pain. Each

statement is provided with a 4-point Likert scale, and total scores range from 17 to 68, with a higher score indicating more fear of movement.

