## **Analysis methods**

### **Primary analysis**

#### *Intention-to-treat analysis:*

The primary analysis of clinical effectiveness will be the assessment of the between-group mean difference in change in hip-related QoL (iHOT-33) from baseline to 6 months after randomization. Between-group mean differences in change larger than 6.1 points will be considered clinically relevant. Consequently, to determine the intervention's effectiveness compared to usual care, the lower limit of the 95% confidence interval for the mean difference must be greater than 6.1 points. Secondary analysis will be the assessment of the between-group mean difference in change in secondary outcomes from baseline to 3 months, 6 months, and 12 months. Assessment of between-group differences in changes will be conducted using a linear mixed-effect model for continuous variables and a generalized linear mixed-effect model for binary variables. This approach accounts for the correlation between repeated measurements within the same patient over time. The model will include fixed effects for the intervention group (physiotherapist-led exercise or usual care) and time points (Baseline, 3, 6, and 12 months). Patients and recruitment sites (Aarhus, Aalborg, Hvidovre, Horsens, or Melbourne) will be included as random effects to account for potential clustering effects. To assess whether the effect of the intervention on hip-related QoL (iHOT-33) varies over time, an interaction term between the intervention group and time will be included. Supplementary, to further guide the clinical interpretation of change in iHOT-33, the between-group difference in the proportion of participants achieving the minimal clinically important difference of 6.1 for within-patient score change was analyzed using an a-priori threshold of 20%. A difference of less than 20% was considered no meaningful difference between treatments, and 20% or greater was considered a meaningful difference. A sensitivity analysis for thresholds of 10% and 30% will be conducted. Supplementary to this interpretation, we will conduct calculations for other identified values of minimal important change by Scholes et al., of 8.7 points, and Kemp et al., of 10.0 points.

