**Pain Kinesiophobia**

TSK-17 (17-68), mean (SD)

FAI: Femoroacetabular Impingement. NSAID: Nonsteroidal Anti-inflammatory Drugs. MET: Metabolic Equivalent.

SQUASH: the short questionnaire to assess health-enhancing physical activity. TSK-17: Tampa Scale of Kinesiophobia.

SD: Standard Deviation. 95% CI: 95% Confidence Interval. MET: Metabolic Equivalent.

If data is not normally distributed median and interquartile range (IQR) will be reported instead of the mean and standard deviation (SD).

**Table 2:** Changes from baseline to 6-month follow-up in primary and secondary outcomes in the intention-to-treat-population.

	Physiotherapist-led exercise (n = )			Usual care (n = )			Difference in change (95% CI)	
	Baseline (95% CI)	6-mo (95% CI)	Change (95% CI)	Baseline (95% CI)	6-mo (95% CI)	Change (95% CI)		
Primary								
iHOT-33, (0-100)								
Secondary								
1-RM Leg Press, Kg								
Index hip								
Non-index hip								
Hop for Distance, cm								
Index hip								
Non-index hip								
One-Leg Rise Test, Reps								
Index hip								
Non-index hip								
PASS (% Yes)								
GPE QoL								
GPE Pain								
GPE ADL								
Hip surgery (%)								

6-mo: 6-month follow-up. 95% CI: 95% Confidence Interval. iHOT-33: International Hip and Outcome Tool 33. 1 RM: 1 Repetition Maximum. Reps: Number of repetitions (0-50). PASS: Patient Acceptable Symptom State. GPE: Global Perceived Effect. QoL: Quality of Life.

**Table 3:** Changes from baseline to 6-month follow-up in the other outcomes in the intention-to-treat-population.

	Physiotherapist-led exercise (n = )			Usual care (n = )			Difference in change (95% CI)
	Baseline (95% CI)	6-mo (95% CI)	Change (95% CI)	Baseline (95% CI)	6-mo (95% CI)	Change (95% CI)	
iHOT-33 subscales, (0-100)							
Symptoms							
Sport							
Job							
Social							
HAGOS subscales, (0-100)							
Pain							
Sport							
Quality of Life							
SQUASH							
Total activity score (MET)							
Light intensity (min/week)							
Moderate intensity (min/week)							
Vigorous intensity (min/week)							
Sport participation							
HSAS, (1-8)							
RTS, (1-4)							

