iHOT-33: International Hip and Outcome Tool 33. Symptoms: Symptoms and Functional Limitations. Sports and Recreational Activities. Job: Job-related concerns. Social: Social, Emotional, and Lifestyle Concerns. HAGOS-Sport: Physical Function in Sport and Recreation. 1 RM: 1 repetition maximum. Cm: centimeters. Kg: Kilograms. PASS: Patient Acceptable Symptom State. HAGOS: The Copenhagen Hip and Groin Outcome Score. SQUASH: the short questionnaire to assess health-enhancing physical activity. TSK-17: Tampa Scale of Kinesiophobia. HSAS: the Hip and Sports Activity Scale. RTS: Return to Sport questionnaire. SD: Standard Deviation. 95% CI: 95% Confidence Interval. MET: Metabolic Equivalent.							

**Table 4:** Costs and effects from baseline to 12-month follow-up in the intention-to-treat population.

	Physiotherapist-led exercise (n = )			Usual care (n = )			ICER/ICUR (95% CI)	
	Baseline (95% CI)	12-mo (95% CI)	Change (95% CI)	Baseline (95% CI)	12-mo (95% CI)	Change (95% CI)		
Effects								
QALYs								
iHOT-33, 0-100								
Healthcare costs (HUQ)								
Number of visits								
Physiotherapist								
General practitioner								
Allied health professional								
Complementary care provider								
Emergency department								
Medical specialist								
Admitted to the hospital								
Hip surgery								
Other healthcare providers								
Healthcare Costs (HUQ)								
Medicine usage								
Prescription 1								
Prescription 2								
Prescription 3								
Productivity Costs (IPCQ)								
Indirect costs								
Absenteeism								
Presenteeism								
Productivity loss								

QALY: Quality Adjusted Life Years. HUQ: Health care utilization questionnaire. IPCQ: The Productivity Costs Questionnaire. iHOT-33: International Hip and Outcome Tool 33. SD: Standard Deviation. 95% CI: 95% Confidence Interval. DKK: Danish Crowns.

**Table 5.** Incremental Cost-Effectiveness Ratios (ICERs), Incremental Cost-Utility Ratios (ICURs), and Distribution of the Joint Cost-Effect Pairs in the Cost-Effectiveness (CE) Plane.

Analysis	Mean cost difference (95% CI)	Mean effect difference (95% CI)	ICUR/ICER	Distribution in CE Plane (%)			
				NE	SE	SW	NW
Main analysis							
iHOT-33							
QALYs							
SA 1: Complete case analysis							
iHOT-33							
QALYs							
SA 2: Imputed data sets							
iHOT-33							
QALYs							
SA 3: Excluding Melbourne							
iHOT-33							
QALYs							

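### SAP Table 3 does not match the SAP's own outcome definitions: return to sport is set out as a single 1-4 score although categories are called for, TSK-17 has no follow-up row, and the HSAS range is mislabelled

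*SAP*

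**What the plan says.** **Return to sport.** The section on the RTS questionnaire cites a consensus statement under which "RTS should be reported in categories from no return to participation in sport through return to sport and, finally, return to performance". It does not list the categories or give them codes. Table 3 has a single RTS row with range 1-4 and no rows for individual categories.

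**Table 3 layout.** Its title is "Changes from baseline to 6-month follow-up in the other outcomes in the intention-to-treat-population". For each arm it has baseline, 6-month and change columns, followed by a between-group difference in change, all with 95% confidence intervals.

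**Effect measure and models.** Under Confidence intervals and p-values: "Results will be expressed as between-group differences in means with 95% confidence intervals". Under Intention-to-treat analysis, differences in change are estimated "using a linear mixed-effect model for continuous variables and a generalized linear mixed-effect model for binary variables". No model for ordered or unordered categories is named.

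**TSK-17.** It is described under Other outcomes: "total scores range from 17 to 68, with a higher score indicating more fear of movement". Timing of outcome assessments places patient-reported measures at baseline, 3, 6 and 12 months and makes no exception for TSK-17. Its only row is in Table 1, the baseline table.

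**HSAS.** The text says "Results will be expressed from 0 (i.e., no recreational or competitive sports) to 8 (i.e., competitive sports at elite level"). Table 3 labels the scale 1-8.

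**The concern.** A table shell tells the programmer what to produce. Where the shell and the outcome definition differ, someone has to choose between them, and that choice should not be made after the data are seen.

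RTS matters most. The clinical question is how many patients in each arm got back to sport, and how many got back to their former level. A mean of category codes does not answer that. It treats the steps between categories as equal, and different distributions can share the same mean.

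For TSK-17, the plan defines an outcome and appears to collect it at follow-up, but provides no place to report the result. For HSAS, the printed range leaves out a level that the text defines.

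**Working it through.** No sample size, power or error-rate figure is involved, and the plan states no number to reproduce. The check sets text against table.

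**1. RTS: what would an analyst following the SAP do?**
- The row carries a numeric range (1-4) and change columns. It has no n (%) and no category rows.
- The default effect measure is a difference in means.
- The models offered are for continuous or binary variables. No cut-point is given that would make RTS binary.
- Where the SAP intends a percentage it marks it: in Table 2, PASS and hip surgery both carry a % sign. RTS in Table 3 does not.
- Taken together, the most natural reading is a linear mixed model on the codes.

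**2. RTS: what could averaging hide?** This is an illustration only. It assumes that 1 is no return and 4 is return to performance, which the SAP does not state.
- Arm A, half at 1 and half at 4: mean = 0.5 × 1 + 0.5 × 4 = 2.5.
- Arm B, half at 2 and half at 3: mean = 0.5 × 2 + 0.5 × 3 = 2.5.
- Difference in means = 2.5 − 2.5 = 0.
- Top category: 50% versus 0%. Bottom category: 50% versus 0%.
- Proportion at 3 or above: 50% versus 50%, a difference of 0.

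The last line shows that a single cut-point can also miss such a pattern. The counts per category are therefore the essential part of the remedy, and one binary comparison cannot replace them.

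**3. TSK-17.**
- The definition is internally sound: 17 items scored 1 to 4 give 17 × 1 = 17 to 17 × 4 = 68.
- Instruments under Other outcomes with a row in Table 3: iHOT-33 subscales, HAGOS, SQUASH, HSAS and RTS.
- Instrument under the same heading without a row: TSK-17.
- The Table 3 footnote does explain the abbreviation ("TSK-17: Tampa Scale of Kinesiophobia"), but it also explains PASS, 1 RM, cm and kg, none of which has a row in that table. The footnote therefore does not show that a row was intended.

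**4. HSAS.**
- Text: 0 to 8, which is 8 − 0 + 1 = 9 levels.
- Table 3: 1 to 8, which is 8 − 1 + 1 = 8 levels.
- The level missing from the label is 0, no recreational or competitive sport.

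**The case against.** **Averaging of RTS is nowhere stated.** This is true. Table 2 uses the same column template for percentages and for the 7-point GPE items, so the columns alone do not prove that a mean is meant. A 1-4 range also fits four category codes, and the binary model could serve a dichotomised RTS. What stands is that the plan gives no cut-point, no category definitions and no category rows, and sets differences in means as the default. Averaging is the likely result, not a stated one. The 1-4 coding in the example is assumed, and the split was chosen to make the means equal, so it says nothing about the size of any effect in this trial.

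**HSAS.** A reader might infer that patients at level 0 will be dropped or recoded. The SAP does not support this. It contains no such rule, the text expressly includes level 0, and a label in an illustrative shell does not alter collected scores.

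**TSK-17.** A reader might infer selective non-reporting. That is not shown. The shells do not cover everything planned: 3- and 12-month analyses of secondary outcomes are foreseen without a shell in Tables 2 and 3. The timing section also refers to the protocol's schedule table, which is not at hand, so a baseline-only measurement cannot be excluded. A row lost in text extraction is possible but unlikely, because the footnote follows the RTS row directly. The mismatch still stands: Table 3 claims to cover the other outcomes, and TSK-17 is defined as one of them.

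**Conclusion.** Table 3 does not agree with the SAP's own definitions in three places of unequal weight.

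- **RTS** is a substantive analysis gap. The plan endorses categories and then sets out a numeric score, with no model or cut-point suited to categories. That the codes would be averaged is a well-supported inference.
- **TSK-17** is a reporting gap. It is an outcome without a follow-up row, on the reading that the general schedule for patient-reported measures applies to it.
- **HSAS** is a clerical error in a range label, with no consequence for patients' data.

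All three concern outcomes below the primary and secondary tiers. The iHOT-33 inference, the sample size and the economic evaluation are untouched. No effect size can be attached to the RTS point, because the SAP does not define the codes. The correction is worth making before analysis because it is cheap and removes a choice that would otherwise be made with the data in view.

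**What to change.** 1. **RTS.** Define the four categories and their codes in the RTS section. In Table 3, replace the single row with n (%) in each category, by arm, at 6 months. Pre-specify one categorical comparison in place of a mean change, for example the between-arm difference in the proportion at return to sport or better, using the binary mixed model already in the SAP. State the cut-point and the scale on which the result is reported.
2. **TSK-17.** Add a row (17-68) to Table 3. If it is measured at baseline only, say so and remove it from the outcomes.
3. **HSAS.** Align the Table 3 label with the 0-8 range in the text.

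The cost is a few table edits, a short definition and one model statement. No new data are needed, and the primary analysis does not change.
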